8.7 Sample Size and Statistical Power

Using 2:1 randomization, we will enroll 50 patients into a USDA Med-style Food Pattern and 25 patients to receive standardized guidance on fiber intake. The analytic aim of this study is to inform potential effect sizes and variance estimates toward the ultimate goal of conducting a definitive phase 3 randomized trial. While 1:1 randomization is more statistically efficient when group variances in outcome are similar, we plan to enroll more participants into the USDA Med-style food pattern intervention to strengthen the precision of estimates of adherence and patient-reported response. Since statistical testing will not be formally conducted, statistical power was not a primary motivation for sizing for this pilot study.¹⁶⁶ However, enrollment of 50 study participants in the USDA Med-style Food Pattern intervention allows a 95% one-sided confidence interval for the intervention adherence rate to exclude rates less than 0.70 if the observed adherence rate is 0.80 or higher in this pilot study.

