8.2 Study Feasibilities Measures

We will assess willingness to randomize as the number of eligible patients that randomized divided by the number of eligible patients (Aim 1). We will provide descriptive statistical summaries of time to complete survey materials, time interacting with the USDA Med-style Food Pattern platform, and changes in estimated weekly meal expenses. These data will be used to inform the future large-scale trial including the number of study sites, recruitment rate/study duration and amount of coordinator effort. The rate of willingness to randomize is unknown but as long as it is at least 20% our study will be successful. We would also want at least 50% of those willing to randomize to be willing to give a blood sample and at least half of those to give stool.

8.3 Treatment Fidelity and Adherence:

The Fred Hutch FFQ is a standard method of dietary intake assessment that has been used in several large-scale cohort studies including the Women’s Health initiative.^{153, 154} The degree of adherence with the USDA Healthy Med-style Food Pattern (Aim 1) will be ascertained by assigning point scores based on the estimated daily amounts of the recommended food groups and subgroups habitually consumed. Full points will be awarded to diets that meet all the

recommendations and partial points to diets that do not. Given that the USDA Healthy Med-style Food Pattern provides recommended amounts for relevant food groups, the adherence score will be based on food consumption data normalized per 100 kcal, much along the lines of the Healthy Eating Index (HEI). The HEI is a 100-point score that measures adherence to the DGA and is the standard measure of diet quality in the US. This approach represents an advance over the 14-item food frequency MEDAS score, which ranks adherence to the Med-style diet pattern using 3 cutpoints: ≤ 7 , 8–9, or ≥ 10 (maximal adherence).¹⁴⁵ The data derived will help us understand the central tendency and variability in Med-style food pattern scores which is critical for determining the sample size of a future trial. Degree of adherence to the different aspects of the medical management regimen will also be used to define per-protocol analysis and be considered as potential mediators and/or effect modifiers in explanatory regression models

8.4 Signal Assessment for Biomarkers:

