8.5 Secondary Statistical Analyses

Binary and categorical endpoints (e.g., adverse events and complications) will be tabulated by intervention group. Time in healthcare will be summarized by group using medians and interquartile ranges, and differences between intervention groups will be summarized using 95% confidence intervals generated from generalized linear regression models appropriate for each type of outcome (e.g., binary, count, continuous, etc.). To examine the sensitivity of adherence to the Med-style Food Pattern on changes in serum biomarkers, we will modify the primary analytic model described for Aim 2 by separately adjusting for a binary indicator of adherence (adherent vs. not) and a graded measure of adherence to intervention. Finally, we will use

mediation analyses to explore the extent to which changes in serum biomarkers over time are mediated through intervention-induced changes in weight and physical activity.

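### Section 8.7: excluding adherence below 0.70 at an observed 40/50 (80%) carries 92.1% confidence, not 95%; the 95% claim holds from 41/50 (82%)

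*Combined protocol and SAP*

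**What the plan says.** Section 8.7 (Sample Size and Statistical Power) sets 2:1 allocation with 50 participants in the Med-style arm and 25 in the fiber arm. It accepts some loss of efficiency against 1:1 allocation in order "to strengthen the precision of estimates of adherence and patient-reported response". It says that power did not drive the sample size, and then gives one numerical justification: the intervention arm of 50 "allows a 95% one-sided confidence interval for the intervention adherence rate to exclude rates less than 0.70 if the observed adherence rate is 0.80", with higher observed rates also covered. The section does not say how the interval will be computed.

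Two other places bear on this. Section 8.2 gives the success criterion as a rate of willingness to randomize: "The rate of willingness to randomize is unknown but as long as it is at least 20% our study will be successful". No such threshold is attached to adherence. Section 8.5 treats adherence as a proportion-type variable when it plans "separately adjusting for a binary indicator of adherence (adherent vs. not) and a graded measure of adherence to intervention", but gives no cut-off for the binary form.

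**The concern.** The sentence claims 95% one-sided confidence that adherence is at least 0.70 once 80% is observed. With 50 participants, 80% is 40 adherent. At that count several standard one-sided 95% lower limits fall below 0.70, which suggests that the stated confidence depends on an approximation that is too optimistic at this sample size.

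Adherence is a primary outcome in Table 2 (Section 6.1), precision of its estimate is the stated reason for unequal allocation, and this is the only number that supports 50 in the arm. The pilot is meant to inform a definitive trial. If 40/50 were observed, a report following Section 8.7 could say that 0.70 was excluded with 95% confidence, while an exact or Wilson analysis of the same data would not exclude it. Because no method is named, that conclusion could turn on a choice made after the data are seen.

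**Working it through.** **Inputs**, all from Section 8.7:
- n = 50 in the Med-style arm.
- One-sided 95% confidence, so z = 1.645.
- Rate to exclude: 0.70.
- Observed rate 0.80 or higher, so the boundary count is 0.80 × 50 = 40.

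**Step 1. Reproduce the plan's figure.** The plain Wald lower limit is p − z·√(p(1 − p)/n).
- 40/50: 0.80 − 1.645 × √(0.80 × 0.20/50) = 0.80 − 1.645 × 0.0566 = 0.7070.
- 39/50: 0.6836.

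So 40/50 is the first count at which plain Wald excludes 0.70. This matches the sentence, which is not an arithmetic slip.

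**Step 2. Other one-sided 95% lower limits.**

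| Limit | 40/50 | 41/50 |
|---|---|---|
| Log-scale Wald | 0.7122 | 0.7353 |
| Plain Wald | 0.7070 | 0.7306 |
| Wald with t(49) quantile | 0.7052 | 0.7289 |
| Wald with continuity correction | 0.6970 | 0.7206 |
| Jeffreys | 0.6956 | 0.7183 |
| Mid-P | 0.6941 | 0.7168 |
| Wilson | 0.6927 | 0.7150 |
| Agresti-Coull | 0.6915 | 0.7136 |
| Logit Wald | 0.6910 | 0.7132 |
| Clopper-Pearson (exact) | 0.6844 | 0.7069 |

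At 40/50 only the first three exceed 0.70. The likelihood-ratio (0.6973) and arcsine (0.6997) limits also fall short. At 41/50 every limit in the table exceeds 0.70.

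**Step 3. Error of the rule, without any interval formula.** Let X be the number adherent, binomial with n = 50. The chance of wrongly excluding the true rate is largest at the edge, 0.70.
- P(X ≥ 40 | 0.70) = 0.0789, so the attained confidence is 1 − 0.0789 = 0.9211.
- P(X ≥ 41 | 0.70) = 0.0402, so the attained confidence is 1 − 0.0402 = 0.9598.

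The smallest count with error of 5% or less is 41, which is 41/50 = 82%.

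**Step 4. Is 0.70 an unlucky point?** Non-coverage of the lower limit at n = 50, over true rates from 0.65 to 0.75 in steps of 0.0005 (nominal 5%):

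| Limit | Mean | Range |
|---|---|---|
| Plain Wald | 7.1% | 4.8–9.9% |
| Wilson | 4.5% | 3.0–6.4% |
| Exact | 3.6% | 2.3–5.0% |

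Plain Wald is too optimistic over most of this range, not only at 0.70.

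**Step 5. Arm size at which the sentence would hold with the exact limit.** At an observed rate of exactly 80%, the exact limit is 0.6907 for 44/55, 0.6962 for 48/60 and 0.7009 for 52/65. Among these sizes, 65 is the first that passes.

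**The case against.** The strongest reply is that the sentence is true for the interval its authors evidently used. It promises a 95% interval, not guaranteed coverage, and the plain Wald limit excludes 0.70 at exactly the stated boundary. Choosing among approximate, score and exact limits is a legitimate preference. Wilson, a possible replacement, itself misses by up to 6.4% at some nearby true rates, so it does not guarantee 95% either. Section 8.6 makes multiple imputation the primary approach to missing data. A pooled rate need not be a whole count out of 50, and its usual interval is of Wald type. Finally, nothing is decided by this number.

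Part of this stands. The figure does reproduce under plain Wald, Wilson is not an exact guarantee, and the practical consequence is small. The objection does not rescue the 95% claim, however. The 7.9% is a binomial tail probability that involves no interval formula, and it applies to the very rate and count that the plan names. For that statement about 0.70, Wilson and the exact limit give the same threshold of 41 and the same 4.0% error; Wilson's behavior at other true rates does not alter this. The imputation point is a reason to state the planning sentence for 50 evaluable participants, not a reason to leave it unchanged.

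**Conclusion.** The concern holds. Section 8.7 states a confidence that the design attains only from 41/50. At 40/50 the attained one-sided confidence against 0.70 is 92.1%, an error of 7.9% against the intended 5%.

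The severity is minor. The threshold moves by one participant, the plan does no formal testing, its stated success criterion is 20% willingness to randomize, and no go/no-go rule depends on adherence. The case for a larger intervention arm does not depend on which limit is used.

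The figures assume a binary adherence indicator, independent participants and all 50 evaluable. Fewer evaluable participants would weaken the statement further: at 32/40, also 80%, even the plain Wald limit is 0.696.

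**What to change.** In Section 8.7, name the one-sided limit for the adherence rate, preferably exact, with Wilson an acceptable alternative that has the same threshold. Then restate the sentence along these lines: with all 50 intervention participants evaluable, the one-sided 95% lower bound excludes adherence below 0.70 if at least 41 of 50 (82%) are adherent (exact bound 0.707; error 4.0% at a true rate of 0.70).

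The cost is SAP wording and a slightly less favorable figure; the sample size stays the same. The exact limit is somewhat conservative. The chance of excluding 0.70, P(X ≥ 40) against P(X ≥ 41), falls from 58% to 44% if true adherence is 0.80, and from 88% to 79% if it is 0.85.

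As a specification note only, which adds no weight to this point: the same edit could state the food-frequency score cut-off and the visit that make a participant adherent. Section 8.3 describes a graded score, and Section 8.5 uses a binary indicator without defining it.

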3.0 Study Aims and Methods

3.1 Study Aims

Aim 1. Conduct a randomized trial (n=75) of the USDA Healthy Med-style Food Pattern intervention versus standardized guidance on fiber intake for patients with diverticulitis to determine feasibility of a larger-scale effectiveness trial focused on long-term clinical outcomes (recurrence and complications). We will examine willingness to randomize and assess adherence to USDA Healthy Med-style Food Pattern.

Aim 2. Explore plasma inflammatory markers in a subset of participants (n=40) (IL-6, IL-1, IL-1 β) and fecal calprotectin as short-term, intermediate inflammatory biomarkers of response to treatment and collect samples for future biomarker study.

The hypotheses underlying the IMPEDE trial include 1) A large-scale trial of the USDA Med-style Food Pattern will be feasible (high rate of patient willingness to be randomized, high rate of adherence to the intervention, improvement in Med-style food pattern scores assessed by a well-characterized food frequency questionnaire (FFQ) [measure of extent of use of the Mediterranean diet], acceptability of study survey burden and follow-up). 2) A USDA Med-style Food Pattern reduces serum and fecal biomarkers of inflammation more than standardized

recommendation to encourage a high-fiber diet. Based on prior studies, we expect reductions in these biomarkers will correlate to lower rates of recurrent diverticulitis.

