4.7 High Fiber Diet Arm

Participants randomized to the High Fiber Diet Arm will be given commonly used patient education pamphlet,¹⁴⁹ describing fiber and high-fiber foods, the rationale for increasing fiber intake, and ways patients can promote greater intake. Based on prior observational studies of incident diverticulitis, at least 25 grams/day of fiber will be recommended for participants.

5.0 Study Schedule Overview, Research Assessments, Medical Record Review, Call Triggers, Withdrawal, Compensation, and Retention

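### The only quantified adherence benchmark is an uncontrolled single-arm rate, and no baseline-adjusted comparison of the FFQ Med-style score between arms is specified

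*Combined protocol and SAP*

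**What the plan says.** Adherence to the Med-style pattern is a primary outcome (section 6.1, Table 2), measured as an FFQ-derived score at baseline, 6 and 12 months. Section 5.1 applies the Table 1 schedule, including the FFQ at those three visits, to all randomized participants.

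Hypothesis 1 (section 3.1) counts among the signs of feasibility an "improvement in Med-style food pattern scores assessed by a well-characterized food frequency questionnaire (FFQ").

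The analysis text on adherence is as follows.

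- Section 8.3 describes a graded score with full and partial points and states its use: "The data derived will help us understand the central tendency and variability in Med-style food pattern scores". It also mentions per-protocol definitions and adherence as a possible mediator or effect modifier.
- Section 8.5 enters adherence, binary or graded, as an adjustment in the biomarker model.
- Section 8.7 gives the only number: 50 in the Med-style arm allow a "95% one-sided confidence interval for the intervention adherence rate to exclude rates less than 0.70 if the observed adherence rate is 0.80" or higher.

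Section 8.4 writes out a longitudinal ANCOVA comparing the arms on IL-6. It extends this model to the other biomarkers and to patient-reported outcomes, which section 6.1 ties to the quality-of-life instruments. The FFQ score is not named.

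The fiber arm receives a pamphlet "describing fiber and high-fiber foods, the rationale for increasing fiber intake, and ways patients can promote greater intake" (section 4.7). Eligibility (sections 4.3 and 4.4) and randomization (section 8.1, by site) take no account of existing diet. No section states which score, at which visit, makes a participant adherent. The MEDAS cutpoints do not fill that gap, because section 4.6 says the fortnightly MEDAS is for feedback and not for assessing adherence.

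**The concern.** Improvement is a change from baseline, and improvement due to the intervention is a change beyond what the comparator produces. A rate in one arm measures neither. Some participants may already eat close to the Med-style pattern at entry. Others may improve because they have joined a diet study. The fiber arm is advised to eat foods that could plausibly raise the same score.

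The larger trial described in section 3.2 needs the two arms' diets to differ. Section 8.7 gives the pilot's analytic aim as informing effect sizes and variances for that trial, but no effect size is planned for the behavior the intervention targets. A reassuring adherence figure could therefore be reported when dietary separation between the arms is small, and the plan commits to no analysis that would show it.

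**Working it through.** **1. The plan's own figure.** Inputs from section 8.7: n = 50, observed rate 0.80 (40/50), one-sided 95% bound.

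- Wald lower bound: 0.80 - 1.645 × sqrt(0.80 × 0.20 / 50) = 0.80 - 0.093 = 0.707. This reproduces the statement.
- It is borderline. At 40/50 the Wilson bound is 0.693 and the exact (Clopper-Pearson) bound 0.684. At 41/50 they are 0.715 and 0.707.

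Nothing in this calculation involves baseline data or the fiber arm.

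**2. Sensitivity to prior diet.** The documents give no baseline adherence rate, so b is assumed. Suppose a share b already meets the definition of adherent and stays there. Then 0.80 = b + (1 - b)c, and the share c of the remainder who must change is (0.80 - b)/(1 - b).

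| Assumed b | Share of the rest who must change |
|---|---|
| 0 | 80% |
| 0.20 | 0.60/0.80 = 75% |
| 0.40 | 0.40/0.60 = 67% |
| 0.60 | 0.20/0.40 = 50% |

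**3. Sensitivity to the fiber arm.** The documents give no fiber-arm rate, so p is assumed, with full retention at 50 and 25. The difference is 0.80 - p, with standard error sqrt(0.80 × 0.20/50 + p(1 - p)/25).

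| Assumed p | Difference | 95% CI |
|---|---|---|
| 0.20 | 0.60 | 0.41 to 0.79 |
| 0.40 | 0.40 | 0.18 to 0.62 |
| 0.60 | 0.20 | -0.02 to 0.42 |
| 0.70 | 0.10 | -0.11 to 0.31 |

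The single-arm bound is 0.707 in every row.

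**4. Precision of the missing contrast on the score.** The 95% half-width, in SD units of the score at 50 and 25, is as follows.

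- Unadjusted: 1.96 × sqrt(1/50 + 1/25) = 1.96 × 0.245 = 0.48 SD.
- Adjusted, assumed baseline correlation 0.5: 0.48 × sqrt(1 - 0.25) = 0.42 SD.
- Adjusted, assumed baseline correlation 0.6: 0.48 × sqrt(1 - 0.36) = 0.38 SD.

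If one in five were lost from each arm (40 and 20 left, also an assumption), the unadjusted half-width would be 1.96 × sqrt(1/40 + 1/20) = 0.54 SD. Adjustment at the same two correlations would give 0.46 and 0.43 SD.

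**The case against.** The strongest reply is that this is a feasibility pilot without formal testing, and that section 8.7 makes a remark about precision rather than a rule. That is right. Section 8.7 itself says: "Since statistical testing will not be formally conducted, statistical power was not a primary motivation for sizing for this pilot study". The only threshold the plan ties to success is 20% willingness to randomize (section 8.2). A reader might infer that 80% adherence passes the intervention, or that adherence is assessed only as a rate. The documents support neither: no pass mark is set, and a graded score is the primary outcome.

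A reader might also infer that people already eating this way will be counted as adherent. That cannot be known, because no cut-off is defined. Nor is open eligibility an error in itself; it is a reasonable choice for a pilot leading to an effectiveness trial. It only makes baseline adjustment matter more.

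The reply can also cite text that leans toward comparison by arm. Section 8.5 tabulates binary endpoints by group and mentions confidence intervals from regression models suited to the outcome type. Section 8.4 speaks of relating the intervention to primary and secondary outcomes. So it would go too far to say the plan rules out using the comparator here. But this text does not supply the contrast. Section 8.5 covers secondary analyses, its example endpoints are adverse events and complications, and its sentence on group differences concerns time in healthcare. The section 8.4 sentence is about sex and gender as exploratory variables. None of it names the FFQ score or a baseline adjustment.

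Finally, the baseline and fiber-arm rates and the correlations above are assumptions. That stands, and they are shown as ranges for that reason.

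**Conclusion.** The point holds as a gap in specification. The one quantified adherence benchmark is an uncontrolled rate in the Med-style arm. The planned work on the score is descriptive, and no baseline-adjusted comparison between arms is written for this primary outcome.

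An observed 80% is compatible with an arm difference of 0.60 or of 0.10 (95% CI -0.11 to 0.31) when the fiber-arm rate is 20% or 70%. It is also compatible with 80% down to 50% of initially non-adherent participants changing, when 0 to 60% were adherent at entry. These figures illustrate what the benchmark cannot distinguish; they do not forecast the result.

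The score contrast can be estimated to about 0.38 to 0.42 SD with baseline adjustment, given a correlation of 0.5 to 0.6 and full retention. That is too wide to detect a small separation, but it is informative for planning the larger trial. The conclusion that the contrast is missing does not depend on any of the assumed values.

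**What to change.** In section 8.3, apply the longitudinal ANCOVA already written for IL-6 in section 8.4 to the FFQ Med-style score. Adjust for baseline score and site, and include the time-by-intervention term so that the Med-style minus fiber difference is given at 6 and 12 months with 95% CI. State that this estimate is what will be used to judge improvement under hypothesis 1. The log transformation in section 8.4 is for skewed biomarkers and need not carry over unless the score is skewed. The missing-data approach of section 8.6 can be used unchanged.

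State the score cut-off and the visit that define adherent, before any data are examined by arm. Report that rate at baseline and at follow-up in both arms. Keep the section 8.7 rate as a descriptive figure and label it a precision statement.

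The cost is some SAP wording and one more model on data already scheduled. No extra visits, participants or formal tests are needed. The adherence result may look less favorable than the single-arm figure alone, and fixing the analysis in advance prevents a choice between the two after the fact.

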8.8 Data and Safety Monitoring Plan (DSMP)

Given the minimal risk nature of this study, monitoring will be conducted by the DCC and an Independent Safety Monitor (ISM). The ISM will review patient-reported outcomes as they accrue over time but will not be responsible for making interim decisions based on observed efficacy (or lack thereof). ISM and the DCC will put together a report according to accrual (at 50%, 75%, and full enrollment). The study team will review and report to the IRB and sponsor as required.

9.0 Study Related SAEs

9.1 Identification of SAEs

Randomized participants will be monitored for SAEs throughout their study surveillance period (enrollment through twelve months). The occurrence of an SAE may come to the attention of study personnel during study follow-up phone interview or by a study participant calling the study team or presenting for medical care. Study staff will use the EMR to fill out the SAE form. The PI will then complete the form and sign the form. The SAE form will then be submitted to the DCC who will provide it to the ISM. The ISM will review the SAE form and ask the study team for additional clarification or specification as he/she sees necessary.

9.2 SAE Reporting

Life-threatening complications or SAEs are a very rare possibility with both intervention arms. SAEs are defined as one of the following conditions (also listed in section 6.2.):

1. Death during the period of protocol-defined surveillance;
2. Life-threatening event related to the treatment or significant disability/incapacity related to the treatment; or
3. Inpatient hospitalization except for:
 - Planned, elective surgical procedures
 - Labor and delivery
 - Psychiatric hospitalizations

All SAEs will be:

1. Recorded on the appropriate SAE case report form;
2. Adjudicated by the ISM;
3. Followed until satisfactory resolution or until the study investigators deem the event to be chronic or the participant to be stable;
4. Reported to the study team and IRBs per their reporting guidelines; and
5. The study investigators will also report SAEs to the funder when appropriate.

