2.0 Background and Rationale

Diverticulitis is one of the most common gastrointestinal indications for inpatient hospital admission, outpatient clinic and emergency room visits, and colon surgery.^{1, 2} At least 20% of individuals with an initial episode of diverticulitis will have one or more painful and unpredictable recurrences.³ The risk of recurrence increases with each subsequent episode.³ Unfortunately, there is no proven pharmacologic means to decrease the risk of diverticulitis.⁴ Currently, secondary prevention relies on segmental colectomy, which is associated with a ~10% risk of major complications and does not eliminate the possibility of future attacks.⁵⁻⁸ In the face of the enormous burden of recurrent diverticulitis, secondary prevention is a high priority.

Diet and lifestyle factors are modifiable targets for prevention of diverticulitis. Multiple large, prospective cohort studies, including work from our group, have identified low dietary fiber, high red-meat intake, and a Western dietary pattern as risk factors for incident diverticulitis.⁹⁻¹³ Physical inactivity, obesity, smoking, and nonsteroidal anti-inflammatory drug use also increase risk.¹⁴⁻¹⁹ An observational study of 51,000 men examining the joint contribution of multiple modifiable risk factors found a linear relationship between number of low-risk factors and diverticulitis incidence. Adherence to a low-risk profile (<51g/day red meat, >23g/day fiber, 2 hours exercise/week, normal BMI and never smoked) decreased the risk of incident diverticulitis by nearly 75% (RR 0.27, 95% CI 0.15-0.48).²⁰ However, these modifiable risk factors have not been evaluated for secondary prevention. Based on the indirect nature of the evidence, U.S. guidelines conditionally recommend diet and lifestyle changes in individuals with a history of diverticulitis. As part of the Dietary Guidelines for Americans, the USDA developed a Healthy Mediterranean-style Food Pattern²¹ that includes the main dietary components associated with primary prevention of diverticulitis and may be effective for secondary prevention. However, barriers to adherence relating to cost, cultural preferences, and food restrictions need to be addressed to consider it a practical intervention in a clinical setting.

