4.4 Exclusion Criteria

Participants must not have any of the following exclusion criteria:

1. Unable or unwilling to return for specimen collection visits or be contacted for and/or complete research surveys;
2. Currently incarcerated in a detention facility or in police custody (patients wearing a monitoring device can be enrolled) at baseline/screening;
3. Last episode of acute diverticulitis currently unresolved (i.e., on antibiotics for diverticulitis; drain in place)
4. Intolerance/allergy to the main components of the Med-style food pattern;
5. Surgery for diverticulitis within past 6 months without an episode of diverticulitis post-surgery
6. Planned elective surgery in next 6 months

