6.2 Clinical Complications

Death, SAEs, and complications (reported as AEs via EMR review) will be assessed and recorded through the study surveillance period. Complications (reported as AEs) will incorporate NSQIP standards and definitions as well as events related to antibiotic-related complications.

Table 3: Summary of SAE/AEs

| Serious Adverse Events | Adverse event |
|--|--|
| Death | |
| Life-threatening event | |
| CVA or stroke | |
| MI requiring treatment or cardiac arrest | Myocardial infarction Atrial arrhythmia |
| Unplanned admit to ICU | |
| Acute Renal Failure (requiring dialysis) | Major UTI (e.g., pyelonephritis) Urinary retention Acute Renal Failure (no dialysis) Progressive renal insufficiency |
| C. difficile colitis (requiring colon resection) | |
| Pulmonary embolism requiring therapy | DVT/PE requiring treatment |
| Coma >24 hours | |
| Septic shock (requiring pressors) | Sepsis |
| Bleeding requiring transfusion | |
| Newly infected prosthetic graft infection | |
| Mechanical ventilation >48 hours | Tracheal reintubation/tracheostomy |
| Colostomy or ileostomy | NG tube replacement (non-routine) Bowel obstruction Ileus |
| | Organ/space infection (including peritonitis) Surgical site infection Intra-ab Abscess Severe dehydration Hernia Malignant hyperthermia Pneumonia Other infection Other post-op occurrence: unspecified Other non-operative intervention: unspecified Unplanned (re)operative intervention during index C. difficile colitis (not requiring colon resect) |

| | |
|------------------------------|--|
| Other life threatening event | |
| Hospitalization* | |

*Exception to hospitalizations that do not need to be reported as an SAE:

- Planned, elective surgical procedures
- Labor and delivery
- Psychiatric hospitalizations

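### The SAE exemption for elective surgery has no limit on timing or indication, so an uncomplicated elective colectomy for diverticulitis decided during follow-up gets no SAE review, and Sections 9.2 and 6.2 disagree on stoma cases

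*Combined protocol and SAP*

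**What the plan says.** Section 9.2 defines SAEs by three conditions: death, a treatment-related life-threatening or disabling event, and "Inpatient hospitalization except for" three categories of admission. The first category is "Planned, elective surgical procedures". No condition is attached on when the operation was planned or what it is for.

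Table 3 in Section 6.2 repeats the carve-out in a footnote to its hospitalization row, introduced as "Exception to hospitalizations that do not need to be reported as an SAE". It too carries no limit on timing or indication. The SAE column of the same table separately lists "Colostomy or ileostomy", along with transfused bleeding, unplanned intensive care admission, septic shock and others. The footnote does not attach to those rows.

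Other relevant provisions:
- Section 4.4, exclusion 6: "Planned elective surgery in next 6 months".
- Section 9.1: SAE surveillance runs from enrollment to twelve months. Individual events travel by form: "The SAE form will then be submitted to the DCC who will provide it to the ISM".
- Sections 9.2 and 9.3: the ISM adjudicates SAEs, and the ISM and the site lead assess whether they are related to treatment.
- Section 2.0: secondary prevention currently rests on "segmental colectomy, which is associated with a ~10% risk of major complications".

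**The concern.** Elective colectomy is a foreseeable event in this population. Section 2.0 describes it as the present means of secondary prevention, and Section 8.0 gives overuse of preventive resection as part of the reason for the trial. An exemption for elective operations usually serves to keep admissions that were already arranged at entry out of the safety data. Here the wording goes further and also covers operations for the disease under study that are decided while the participant is on an assigned diet.

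At stake are the three steps that follow from an SAE form: review by the ISM while the trial is running, adjudication, and an assessment of relatedness. An exempt admission gets none of them as an SAE. The SAE table would also omit some diverticulitis-related hospitalizations, in either arm. In addition, two definitions that are meant to match give different answers when the operation includes a stoma, so the same event could be classified in two ways.

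**Working it through.** This is a comparison of texts. The plan states no figure to reproduce, and the only arithmetic is on the time windows.

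**1. Is there a limit anywhere?** Section 9.2, the Table 3 footnote, the outcome table (Table 2), the record review section (5.3), the monitoring plan (8.8) and Sections 9.1 and 9.3 were read together. None restricts the exemption by date of planning or by indication.

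**2. Which operations can the exemption cover?** Surveillance lasts 12 months (Section 9.1). Exclusion 6 covers surgery planned for the next 6 months (Section 4.4).
- Months 0–6: a participant with an operation already planned for this window should not have been enrolled. The exemption therefore applies to operations decided after screening.
- Months 6–12 (12 − 6 = 6 months): an operation may have been planned before enrollment or decided later.

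So for 6/12, or half, of the surveillance period, the exemption has essentially no already-arranged surgery to act on. This assumes that eligibility was applied correctly and that no operation planned for after month 6 was brought forward.

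**3. How is each case classified?**

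| Case, decided after enrollment | Section 9.2 alone | Table 3 |
|---|---|---|
| Elective colectomy, no stoma, no listed complication | Exempt | Exempt by footnote |
| Elective colectomy with stoma | Arguably exempt | SAE in its own right |
| Elective colectomy with a listed complication such as transfused bleeding or septic shock | SAE only if another 9.2 condition is met | SAE in its own right |
| Unplanned inpatient admission for diverticulitis before the operation | SAE | SAE |

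The first row is the gap. The second and third rows show the conflict: Section 9.2 points to Section 6.2 as carrying the same list, yet Table 3 is broader.

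**4. What happens to the first-row case?** There is no SAE form, hence no individual report to the ISM under Section 9.1, no adjudication under 9.2 and no relatedness assessment under 9.3. The operation can still be recorded as a diverticulitis event leading to surgery (Table 2, quarterly) and through record review, which captures surgery type (Section 5.3). The documents do not say that the ISM receives those records event by event. Section 8.8 has the ISM review patient-reported outcomes as they accrue. Its reports are tied to accrual, at 50%, 75% and full enrollment, and none is scheduled afterwards, when the last participants still have most of their follow-up ahead.

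**The case against.** The best case for leaving the text alone is that the gap is narrow and the data are not lost. The exemption attaches only to the hospitalization criterion. A stoma or a listed complication is an SAE under Table 3 whether or not the operation was elective, an unplanned diverticulitis admission that leads to surgery is reportable, and Table 2 sends a subset of surgical complications, including return to the operating room, to the ISM. The trial describes itself as minimal risk, and the ISM makes no interim decisions on efficacy. All of this stands, and it confines the point to the first-row case and the conflict on stomas and complications.

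Three stronger readings are tempting, and the documents support none of them.
- A reader might infer that an elective colectomy for diverticulitis never reaches the ISM. The routes just listed show otherwise.
- A reader might infer from exclusion 6 that an operation in months 0–6 was chosen because the disease worsened on the assigned diet. Exclusion 6 shows only that it was not planned at screening. Participants are recruited partly from surgery clinics (Section 4.2), may have recurrent disease and may be up to 18 months past an episode (Section 4.3). Patient preference or earlier history could equally explain the decision. Sorting this out is the task of the relatedness assessment that the exemption bypasses.
- A reader might want an expected number of missed events. The documents give no elective colectomy rate. Applying an assumed rate to all 75 participants would also count stoma cases and operations planned before enrollment, so it would not measure this gap.

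**Conclusion.** The point holds in a limited form. Followed exactly, the plan leaves one type of disease-related hospitalization outside SAE review: an elective colectomy for diverticulitis decided during follow-up, with no stoma, no listed complication and no preceding unplanned admission. Exclusion 6 makes the breadth of the exemption harder to justify, because in half of the surveillance window the exemption reaches essentially only surgery decided after screening. Separately, Sections 9.2 and 6.2 give different answers for a colectomy with a stoma and must be reconciled.

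The number of participants affected cannot be derived from the documents. The conclusion rests on the wording of the exemption, on correct application of exclusion 6, and on the absence of any stated route by which the ISM sees non-SAE surgery individually. It does not rest on any claim that such surgery reflects failure or harm of the assigned diet. This is a gap in safety reporting that should be closed. It does not affect the primary feasibility outcomes, and the surgery itself remains in the trial data.

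**What to change.** Reconcile Section 9.2 with Table 3 so that one SAE list governs, and say explicitly how a stoma or a listed complication after elective surgery is classified.

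In both places, limit the hospitalization exemption to elective procedures planned before consent or unrelated to diverticulitis. Admissions for diverticulitis surgery decided after enrollment would then be reported on the existing SAE form to the existing ISM.

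This alters what is reported and leaves every surgical and treatment decision as it is. The cost is one sentence in two places and a few more SAE forms, some for admissions already recorded on the Healthcare Utilization Form.
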